## PROTOCOL SYNOPSIS version dated 12/20/2022

**Brief Summary:** Endometriosis affects an estimated 10-15% of people assigned female at birth and is one of the most common causes of chronic pelvic pain. The disease impairs overall quality of life, directly affects many domains of physical and emotional functioning, and can be a tremendous economic burden. Endometriosis is responsible for an estimated \$69.4 billion per year in excess health expenditures and costs \$12,118 per patient per year in the United States. Additionally, people with endometriosis lose an average of 6.3 hours of workplace productivity and 4.9 hours of household productivity per week. The current mainstays of endometriosis treatment often fail leading to patients experiencing recurrent pain and needing re-intervention and repetitive surgeries. The need for implementation of more effective treatments for endometriosis-associated pain is great.

Group care has been effectively used to manage chronic back and neck pain, fibromyalgia, and headaches. Moreover, Chao et al. enrolled 26 people with female chronic pelvic pain into a group care program *Centering Chronic Pelvic Pain (Centering CPP)*. The authors reported before-and-after assessments revealing that attendance at  $\geq 4$  sessions was associated with fewer unhealthy days per month (24 to 18,  $P < 0.05$ ), fewer depressive symptoms (12 to 9,  $P < 0.05$ ), and lower symptom severity (4.2 to 3.1,  $P < 0.01$ ).

To adapt *Centering Chronic Pelvic Pain* to be specific to patients with endometriosis, I assembled an interdisciplinary team of collaborators: [name], an expert in chronic pain clinical psychology; [name] and [name], an expert in women's health physical therapy; and [name], an expert in yoga, physical therapy, and group care. Together we developed Peer-Empowered Endometriosis Pain Support (PEEPS), which integrates three evidence-based approaches. 1) Physical therapy improves the pelvic floor and musculoskeletal components of pain, 2) Mindfulness interventions improve global impression of change, overall quality of life, and anxiety and depression, 3) Yoga reduces pain and improves emotional well-being and sexual function. Given that PEEPS combines an interdisciplinary team approach, an integrative setting, and group care into one program incorporating evidence-based components, it is likely to be an effective strategy to treat patients with endometriosis-associated pain. However, since these evidence-based interventions have not been bundled and delivered in this way before, effectiveness of this approach must be evaluated. Given the urgent need for translation of effective treatments into practice, I will take an implementation science approach to understand the implementation outcomes of PEEPS and the implementation context (or barriers and facilitators) of PEEPS.

Here, I propose to conduct a pilot clinical trial in which 40 patients with endometriosis and chronic pelvic pain attend PEEPS in addition to usual care. Within this trial, I will test the **central hypothesis** that PEEPS will lead to decreased endometriosis-related pain interference, improved quality of life, and decreased pain catastrophizing by pursuing the following **specific aims**:

**Aim 1: Measure preliminary effectiveness of PEEPS.** I will use validated patient-reported outcomes measures to assess preliminary effects on pain interference and quality of life. I **hypothesize** that patients in PEEPS will show decrease in pain interference in daily activities at program completion and 6-months post-completion than at baseline. With 40 patients attending PEEPS this pilot trial will assess both preliminary effectiveness as well as implementability of PEEPS.

**Aim 2: Assess PEEPS implementation factors.** 2a. Evaluate barriers and facilitators to PEEPS success. I will use an implementation science approach to expedite translation of PEEPS to the clinical setting. I will use the *Intervention Characteristics* (e.g. relative advantage, complexity, design quality) and *Process* (e.g., Planning, Reflecting and Evaluating) domains from CFIR to identify barriers and facilitators to PEEPS implementation at the patient and provider levels. 2b. Assess implementation outcomes of PEEPS. Guided by Proctor et al.'s *Implementation Outcomes Framework* and new guidance for CFIR, I will evaluate acceptability, appropriateness, and feasibility of PEEPS implementation. These outcomes will be measured through participant attendance, group flow and patient and facilitator feedback on individual sessions and the program as a whole.

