- Modified Everyday Discrimination Scale: validated, 9 questions, with 10 follow up questions if discrimination ongoing to assess experiences of healthcare discrimination
- Personal goals: I will ask participants to identify three personal goals related to quality of life that they hope to achieve by participating in PEEPS, such as “Be able to go on a hike without pain limiting my activity”.

Patients will receive a unique link to their questionnaires at each of the three time points. Participants who do not respond will be sent three reminder messages and receive up to two completed phone call reminders. The research team will be responsible for day-to-day study supervision and data management. The study statistician will perform monthly data quality control analysis for missing values and data discrepancy and create monthly data reports on screening and recruitment. Data security will be maintained by using dedicated password-protected, encrypted computers with multiple backups.

**1.3. Analysis plan:** This is a pilot observational trial of a novel intervention where preliminary effect size is unknown. Recommendations for pilot clinical trials suggest using 12-70 subjects. Enrolling 40 subjects will reduce imprecision around the standard deviation estimate and allow for sufficient participants in PEEPS to assess implementation factors. We hypothesize that patients engaging in PEEPS will experience less pain interference after completing PEEPS than at baseline. Descriptive statistics and two-sample t-test will be performed for numeric variables with normal distribution, Wilcoxon Rank Sum test if not normal distribution. Frequency analysis and Fisher exact or Chi-square test for categorical variables will be performed as appropriate. Longitudinal analysis on primary outcomes and secondary outcomes using paired t-test

comparing each time point (completion and 6-months) to baseline. Mixed effects model will be used for fixed effect of PEEPS compared to baseline over time with random effect of intercepts. For categorical outcomes, we will calculate relative risk and 95% confidence intervals.

**1.4. Feasibility of recruitment and retention:** Patients will receive \$25 for completion of the baseline questionnaire and \$50 for each of the two other time points (completion and 6-months). Patients who complete all portions of the study will receive a total of \$125.

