Design quality	Perceived excellence of intervention, format, and content	Patient/Clinician	· Validated, Quantitative, Qualitative 	
Process				Aim 2a CFIR
Planning	Quality of intervention delivery method	Patient/Clinician	· Quantitative, Likert scale · Suggestions for improvement, Qualitative	

Program execution	Carrying out intervention according to plan	Patient/ Clinician	· Validated, Quantitative, Qualitative 	
Reflecting & Evaluating	Feedback on experience with intervention	Patient	· Most helpful part, Qualitative · Least helpful part, Qualitative	
Acceptability	Stakeholder perception if PEEPS is agreeable/ satisfactory	Patient/ Clinician	· Satisfaction with intervention- Validated, Quantitative, Qualitative  · Likelihood of recommending to peer Quantitative, Likert scale	Aim 2b IOF
Appropriateness	Perceived fit, relevance, and compatibility of PEEPS Perceived cultural appropriateness of PEEPS	Patient  Clinician	· Appropriateness of material, Validated, Quantitative  · Session flow, Validated, Qualitative  · Participant engagement, Qualitative · Group dynamics, Qualitative	Aim2b IOF
Feasibility	Extent to which PEEPS can be successfully carried out	Patient	· Administrative data on recruitment, enrollment, retention, Quantitative	Aim 2b IOF

CFIR, Consolidated Framework for Implementation Research; IOF, Proctor's Implementation Outcomes Framework.

**2.2. Outcome measures:** After completion of all PEEPS sessions, we will use a mixed methods approach that includes descriptive statistics and content analysis. Categorical survey outcome data will be analyzed using chi-square or Fisher's exact tests as appropriate. Ordinal survey outcome data will be analyzed using the Mann-Whitney U test. A p-value of 0.05 will be used to assess significance. Qualitative data from open-ended survey responses will be entered and analyzed in NVivo 12 software. Qualitative data will be analyzed for *a priori* and emerging themes. We will examine satisfaction using sentiment analysis of major and sub-themes. We will then triangulate the quantitative and qualitative data to gain insight on the constructs measured in Table 2. These findings will be used to optimize PEEPS in preparation for the definitive multi-center effectiveness RCT.

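### The central hypothesis is causal, but every longitudinal comparison that Aim 1 specifies is with the patient's own baseline, so a fall in pain interference cannot be credited to PEEPS

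*Combined protocol and SAP*

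**What the plan says.** The synopsis sets out to test the central hypothesis that "PEEPS will lead to decreased endometriosis-related pain interference, improved quality of life, and decreased pain catastrophizing", in a pilot in which "40 patients with endometriosis and chronic pelvic pain attend PEEPS in addition to usual care". Section 1.1 likewise recruits forty patients to the 8-week programme and mentions no control group.

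Section 1.3 (Analysis plan) describes the study this way: "This is a pilot observational trial of a novel intervention where preliminary effect size is unknown". Its hypothesis is a before-after statement: "We hypothesize that patients engaging in PEEPS will experience less pain interference after completing PEEPS than at baseline". The method is "Longitudinal analysis on primary outcomes and secondary outcomes using paired t-test", with completion and 6 months each set against baseline. A random-intercept mixed model follows, whose fixed effect is named as that of PEEPS relative to baseline. A two-sample t-test is listed, but no groups are named for it. Section 1.3 states no control comparison, repeated baseline or caveat on interpretation.

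Two other places describe a different design. Section 2b calls the study a pilot RCT. Protection of Human Subjects, Section 1a, randomizes patients to PEEPS plus usual care or usual care alone, and recruits until 30 in the PEEPS arm have attended at least one session.

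**The concern.** To say that a programme leads to improvement is to compare it with what would have happened without it. A patient's own baseline does not supply that. The mean change contains any effect of PEEPS, but also concurrent usual care, the natural course of the disease, reporting effects in an unblinded group programme, and regression to the mean.

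The last of these has some footing in the documents. Patients come by clinician referral from gynaecology clinics, one of them a sub-specialty referral practice. Sections 1b and 2b of Protection of Human Subjects say that pain exacerbations are often unpredictable and sporadic. If patients are more likely to be referred or to join during a bad spell, some will improve without any intervention.

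What is at stake is the conclusion. Followed as written, the plan lets a significant paired t-test be reported as confirming the central hypothesis, and the model output be labelled an effect of PEEPS. The analysis supports neither statement.

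**Working it through.** **The plan's own figure.** N = 40 rests on two statements in Section 1.3: "Recommendations for pilot clinical trials suggest using 12-70 subjects" and "Enrolling 40 subjects will reduce imprecision around the standard deviation estimate". Aim 1 gives no effect size, SD, power, alpha or dropout rate, so 40 cannot be recomputed. It lies within 12 to 70, and nothing here says it is wrong.

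**Inputs for the illustration**
- n = 40: synopsis and Section 1.1.
- Paired t-test against baseline: Section 1.3.
- Two-sided alpha 0.05: assumed. Section 2.2 states 0.05 for the Aim 2 surveys only.
- True PEEPS effect: zero, by construction.
- r, the baseline-to-follow-up correlation: assumed 0.5 to 0.8.
- k, how far the enrolled group's mean at the baseline survey sits above its usual level, in SDs: assumed 0 to 0.8.

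**Formulas**
- Expected spurious fall = k(1 − r) baseline SDs.
- SD of the change = √(2(1 − r)) baseline SDs.
- Noncentrality = √40 × k(1 − r) / √(2(1 − r)).
- Chance of a significant improvement = P(T > 2.023), with T noncentral t on 39 df.

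**Smallest significant fall.** 2.023/√40 = 0.32 SD of the change. At r = 0.7 the SD of the change is √0.6 = 0.775, so this is 0.32 × 0.775 = 0.25 baseline SDs.

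**One case in full (r = 0.7, k = 0.8).** Spurious fall = 0.8 × 0.3 = 0.24 SD. Noncentrality = 6.325 × 0.24/0.775 = 1.96. Chance = 48.1%.

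**Chance of a significant improvement with no PEEPS effect, n = 40**

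| Entry excess k | r = 0.8 | r = 0.7 | r = 0.5 |
|---|---|---|---|
| 0 | 2.5% | 2.5% | 2.5% |
| 0.3 SD | 8.5% | 10.7% | 15.0% |
| 0.5 SD | 16.2% | 22.2% | 33.8% |
| 0.8 SD | 34.5% | 48.1% | 69.4% |

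For k of 0.3 to 0.8 the spurious fall runs from 0.3 × 0.2 = 0.06 SD to 0.8 × 0.5 = 0.40 SD.

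**Sensitivity to baseline timing.** Simulation (20,000 runs per cell) enrolled patients only from the upper half of scores. With the baseline survey taken at that same moment, the rates were 36%, 52% and 77% for r = 0.8, 0.7 and 0.5. With a gap before the survey that halves the transient excess, they fell to 12%, 16% and 24%. If the excess has gone by the survey, the rate is about 2.5%.

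**Is the missing comparator the cause?** The same upper-half selection with no treatment effect, but with a randomized usual-care arm and a two-sample t-test on change, gave 2.5% to 2.6% in favour of PEEPS, at 20:20 and at 40:40. The nominal rate is 2.5%.

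**The case against.** The strongest reply is that this is a pilot that claims little. Aim 1 is titled as preliminary effectiveness, Section 1.3 calls the study observational, and the Aim 1 hypothesis is already worded as a change from baseline. An uncontrolled pilot of this kind is common. All of that stands, and it narrows the point to two pieces of text: the causal central hypothesis in the synopsis and the mixed-model term that credits change to PEEPS.

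The size is also open to challenge. Eligibility requires pain of at least 6 months but sets no minimum score. Recruitment includes record pre-screening and telephone approach, and the baseline survey may follow enrolment by some weeks. Entry excess could therefore be small or absent, and the 2.5% row belongs in the table for that reason. A reader might infer that regression to the mean will produce a false positive here. The documents support only that it can. The attribution problem remains even at zero excess, because usual care and natural course are still in the change.

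A reader might also infer that the before-after mean will be used to size the later trial, because Section 2.2 says "These findings will be used to optimize PEEPS in preparation for the definitive multi-center effectiveness RCT". That sentence refers to the Aim 2 implementation findings and to refining the programme. No passage proposes sizing a trial on the Aim 1 mean change, and the stated statistical reason for 40 patients is the SD.

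Finally, the one-arm premise is not settled. If the randomized text is the intended design, a comparator exists and the defect moves: Section 1.3 then lacks a specified between-arm comparison.

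**Conclusion.** The point holds in limited form. In the design of the synopsis and Sections 1.1 and 1.3, the specified longitudinal analysis cannot test the causal hypothesis, because all its comparisons are with the patient's own baseline. That conclusion follows from the text and needs no assumed values.

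The size of the regression-to-the-mean component does depend on assumptions. The false-positive chance runs from 2.5% with no entry excess to 69.4% at 0.8 SD excess and correlation 0.5. Excess, correlation and the Aim 1 alpha are all assumed, and a gap between enrolment and the baseline survey would lower the figures. They show what could happen and do not predict it.

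**What to change.** 1. **Reconcile the design first.** The synopsis and Sections 1.1 and 1.3 (one arm, observational, 40 patients) conflict with Section 2b and Protection of Human Subjects, Section 1a (pilot RCT with a usual-care arm, 30 PEEPS attenders). State one design throughout.
2. **If one-arm:** reword the central hypothesis and the mixed-model term as within-person change in participants receiving PEEPS plus usual care. Report the mean change at completion and at 6 months with 95% CIs, and state that it is not attributable to PEEPS alone.
3. **If randomized:** make the between-arm comparison of change from baseline the Aim 1 analysis in Section 1.3, and name the two groups.

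**Cost.** Option 2 changes wording only: no extra patients, visits or arm. The downside is a more modest claim. Option 3 adds nothing to a design that already randomizes, but precision would be limited. Assuming 1:1 allocation, 80% power and two-sided 0.05, the detectable between-arm difference is (1.96 + 0.84) × √(2/n) in SDs of the outcome compared: 0.89 SD at 20 per arm and 0.72 SD at 30 per arm. Estimation with a confidence interval would suit a pilot better than a test in that case too.

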## APPROACH

### Aim 1: Measure preliminary effectiveness of PEEPS

**1.1. Patient population and recruitment:** This pilot clinical trial will be conducted through the Department of OB/GYN at WUSTL. Forty patients will be recruited to participate in an 8-week curriculum of PEEPS. To equitably recruit a diverse group of participants, including those historically excluded from research, we will recruit from three sites: WUSTL Minimally Invasive Gynecologic Surgery (MIGS) (a sub-specialty referral practice), WUSTL General OB/GYN clinics, and Affinia Healthcare (a Federally Qualified Health Center). If a patient is eligible and elects to participate, written informed consent will be obtained in person while at a clinic visit, or via email or fax when the study is discussed by phone.

#### Inclusion and exclusion criteria:

Inclusion criteria	Exclusion criteria

• Age 18-48 years

• Operative confirmation of endometriosis

• Chronic pelvic pain (defined as pain perceived to originate from the pelvis, lasting <math>\geq 6</math> months)

• No plan to have surgery in next 12 weeks

• Be able to attend eight 2-hour weekly sessions on the WUSTL campus

	

• Non-English speaking

• Currently pregnant

• Severe physical impairment

• History of hip, back, or spine surgery

• Opioid use <math>\geq 5</math> days in the past 3 months, other than for the 6-week post-operative period

• Current or history of psychiatric disorder with psychosis

**1.2. Data collection:** Participants will be recruited for sequential 8-week PEEPS cohorts with a goal of 6-10 subjects in each cohort. At baseline, we will collect data on medical and psychosocial history, and prior and current treatments for endometriosis (medications, physical therapy, surgery, counselling, alternative therapies). Participants will complete baseline questionnaires prior to the first session of PEEPS, within one month of PEEPS completion, and at 6-months post-completion. Surveys will be administered in Research Electronic Database Capture (REDCap), and the following measures will be administered:

- PROMIS pain interference SF 8a: validated, 8 questions, assesses pain interference in daily activities
- PROMIS pain intensity: validated, 3 questions, measures pain on a 1-5 scale over the past 7 days
- Endometriosis Health Profile-30: validated, 30 questions, endometriosis-related quality of life measure
- PROMIS Physical Function SF10a: validated, 10 questions, measures physical activities of daily living
- PROMIS Anxiety SF7a: validated, 7 questions related to anxiety in past 7 days
- PROMIS Depression SF8b: validated, 8 questions related to depression in past 7 days
- Female Sexual Function Index: validated, 19 questions
- Pain Catastrophizing Scale: validated, 13 questions
- Patient Global Impression of Change: validated, 1 question, on a 0-10 continuous scale
- Modified Everyday Discrimination Scale: validated, 9 questions, with 10 follow up questions if discrimination ongoing to assess experiences of healthcare discrimination
- Personal goals: I will ask participants to identify three personal goals related to quality of life that they hope to achieve by participating in PEEPS, such as “Be able to go on a hike without pain limiting my activity”.

Patients will receive a unique link to their questionnaires at each of the three time points. Participants who do not respond will be sent three reminder messages and receive up to two completed phone call reminders. The research team will be responsible for day-to-day study supervision and data management. The study statistician will perform monthly data quality control analysis for missing values and data discrepancy and create monthly data reports on screening and recruitment. Data security will be maintained by using dedicated password-protected, encrypted computers with multiple backups.

**1.3. Analysis plan:** This is a pilot observational trial of a novel intervention where preliminary effect size is unknown. Recommendations for pilot clinical trials suggest using 12-70 subjects. Enrolling 40 subjects will reduce imprecision around the standard deviation estimate and allow for sufficient participants in PEEPS to assess implementation factors. We hypothesize that patients engaging in PEEPS will experience less pain interference after completing PEEPS than at baseline. Descriptive statistics and two-sample t-test will be performed for numeric variables with normal distribution, Wilcoxon Rank Sum test if not normal distribution. Frequency analysis and Fisher exact or Chi-square test for categorical variables will be performed as appropriate. Longitudinal analysis on primary outcomes and secondary outcomes using paired t-test

comparing each time point (completion and 6-months) to baseline. Mixed effects model will be used for fixed effect of PEEPS compared to baseline over time with random effect of intercepts. For categorical outcomes, we will calculate relative risk and 95% confidence intervals.

**1.4. Feasibility of recruitment and retention:** Patients will receive \$25 for completion of the baseline questionnaire and \$50 for each of the two other time points (completion and 6-months). Patients who complete all portions of the study will receive a total of \$125.

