## PROTECTION OF HUMAN SUBJECTS

### 1. Risk to Human Subjects

**1a. Human Subjects Involvement, Characteristics, and Design.** This study is a pilot randomized controlled trial of people with endometriosis-related chronic pelvic pain. Patients meeting inclusion criteria will be enrolled from the outpatient OB/GYN clinic setting. Patients will be recruited for sequential 8-week PEEPS cohorts with a goal of 6-10 subjects participating in each cohort. Enrolled patients will be randomized to PEEPS plus usual care versus usual care alone. Recruitment and randomization will continue until 30 participants in the PEEPS arm attend at least one PEEPS session. Randomization will occur in REDCap with the assistance of the study statistician.

**1b. Study Procedures, Materials, and Potential Risks.** This study will involve collection of data from two key components.

1) Clinical data collection: Relevant clinical and demographic data will be abstracted from medical records including medical and psychosocial history, and prior and current treatments for endometriosis (medications, physical therapy, surgery, counselling, alternative therapies). This data will be abstracted from the patients medical records. For all subjects, these data will be stored in a secure, password-protected REDCap database anonymized with study identifier only. No private identifiable information will be collected.

2) Survey data collection: Subjects in both arms will complete surveys at baseline (defined as the month leading up to the first PEEPS session for their cohort), PEEPS completion, and 6- and 12-months after completion. The validated patient-reported outcomes measures will assess pain severity, physical function, history of sexual trauma, mood symptoms, other quality of life measures, and experiences of discrimination in healthcare. This survey data will also be collected and stored in the password-protected REDCap database.

The proposed study involves potentially rare risks to the subjects, including loss of confidential health information, musculoskeletal injury to patients while participating in the yoga and physical therapy components, emotional distress in completing validated surveys on mental health, and excessive demands on patients. Patients with endometriosis and chronic pelvic pain have intermittent pain exacerbations, sometimes due to common triggers such as menses, ovulation, or intercourse, but many exacerbations are unpredictable and

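### In the one-arm design the mixed model's PEEPS term is only a before-after change, and the random intercept can misstate standard errors at separate visits if correlation falls with time

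*Combined protocol and SAP*

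**What the plan says.** Section 1.3 (Analysis plan) describes the study this way: "This is a pilot observational trial of a novel intervention where preliminary effect size is unknown". It plans two longitudinal analyses. The first is "Longitudinal analysis on primary outcomes and secondary outcomes using paired t-test", "comparing each time point (completion and 6-months) to baseline". The second is "Mixed effects model will be used for fixed effect of PEEPS compared to baseline over time with random effect of intercepts". It does not say how time is coded, what residual covariance or degrees of freedom apply, or which analysis governs if the two disagree.

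The synopsis describes one group, in which "40 patients with endometriosis and chronic pelvic pain attend PEEPS in addition to usual care". Its Aim 1 hypothesis names two separate time points, program completion and 6 months later. Section 1.2 sets three surveys: "Participants will complete baseline questionnaires prior to the first session of PEEPS, within one month of PEEPS completion, and at 6-months post-completion".

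Protection of Human Subjects describes another design. Section 1a says "Enrolled patients will be randomized to PEEPS plus usual care versus usual care alone", and section 1b sets surveys in both arms at baseline, "PEEPS completion, and 6- and 12-months after completion". The Implementation Outcomes Framework paragraph in Aim 2b also calls the study a pilot RCT.

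**The concern.** There are two separate problems with the mixed-model sentence.

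The first is what the PEEPS term estimates. If all 40 participants receive PEEPS, an indicator for PEEPS is an indicator for any survey after baseline. A statistician could fit that indicator alone, add it to a visit factor, or add it to a linear time trend. The first gives one averaged change, the second cannot be estimated, and the third depends on an extrapolation. Only the first is a plain before-after change, and it does not answer the two-time-point hypothesis.

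The second arises if the model does give a contrast at each visit. A random intercept with independent residuals imposes one variance and one correlation on all three visits. Baseline to completion is about 2-3 months (an 8-week programme, then a survey within a month). Baseline to the last survey is about 8 months. If scores further apart are less alike, the model applies an averaged standard error to both contrasts: too small at 6 months and too large at completion. At stake is the reliability of the 6-month result, and which of two planned analyses a reader should believe.

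**Working it through.** **Inputs from the documents.** n = 40; three surveys at roughly months 0, 2-3 and 8; a random-intercept model. The plan's own figure of 40 cannot be re-derived, because section 1.3 supports it only with a recommended range of 12-70 and the precision of the SD. No effect size, SD, power or correlation is given. **Assumed:** two-sided 5% tests (0.05 is stated only for the Aim 2 surveys), equal variances, complete data, and the correlations below.

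**Step 1: can the PEEPS term be estimated?**
- One arm, visit as a factor: the columns are intercept, completion, 6-month and PEEPS. PEEPS = completion + 6-month, so the rank is 3 of 4 and PEEPS has no separate estimate.
- One arm, linear time at months 0, 3, 8: rank 3 of 3, but the PEEPS coefficient is -1.0 x baseline + 1.6 x completion - 0.6 x 6-month. It projects the completion-to-6-month slope back to baseline, which the data cannot check.
- Two arms with a common baseline, visit terms and arm-by-visit terms: rank 5 of 5, so the effect is separable.

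**Step 2: standard errors of separate visit contrasts.** Let r01, r12 and r02 be the correlations for baseline-completion, completion-6 months and baseline-6 months, r their mean, and s2 the variance at each visit.
- Model variance of a change from baseline: 2 x s2 x (1 - r)/n.
- True variance: 2 x s2 x (1 - r0j)/n, where r0j is r01 or r02.
- Ratio of model SE to true SE: sqrt[(1 - r)/(1 - r0j)].

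For 0.7/0.6/0.5, r = 0.6. Completion: sqrt(0.40/0.30) = 1.15. Six months: sqrt(0.40/0.50) = 0.89, so the SE is about 11% too small.

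**Step 3: a single pooled post-baseline effect.** With s2 = 1, the true variance (times n) is 1.5 + 0.5 x r12 - r01 - r02, and the model variance is 1.5 x (1 - r). For 0.7/0.6/0.5 both equal 0.60 (1.5 + 0.3 - 1.2, and 1.5 x 0.4), so the ratio is 1.00.

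**Step 4: range.** SE ratio, then simulated type I error at n = 40:

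| r01 / r12 / r02 | Completion | 6 months | Pooled |
|---|---|---|---|
| 0.6 / 0.6 / 0.6 | 1.00, 5.0% | 1.00, 5.1% | 1.00, 5.1% |
| 0.7 / 0.65 / 0.6 | 1.08, about 3.5% | 0.94, 6.3-6.9% | 1.00, 5.0% |
| 0.7 / 0.6 / 0.5 | 1.15, about 2.5% | 0.89, about 8% | 1.00, 5.0% |
| 0.8 / 0.6 / 0.5 | 1.35, 0.9% | 0.86, about 9% | 1.05, 4.0% |
| decay 0.90 per month (months 0, 3, 8) | 1.24, 1.7% | 0.86, 9.2% | 0.99, 5.1% |
| decay 0.95 per month (months 0, 3, 8) | 1.28, 1.2% | 0.84, 9.9% | 0.98, 5.3% |
| 0.5 / 0.7 / 0.4 | 0.97, 6.0% | 0.88, 8.3% | 0.86, 9.1% |

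The last row is a different pattern, in which the two later surveys resemble each other more than either resembles baseline. It is the only row where the pooled term is clearly affected.

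**Step 5: the planned paired t-tests.** Their simulated type I error stays near 5% in every pattern (4.8-5.2%). Under 0.7/0.6/0.5, power at completion for an assumed 0.3 SD change is about 67% with the paired test and 56% with the random-intercept contrast.

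**The case against.** The strongest reply is that section 1.3 already plans paired t-tests of completion and of 6 months against baseline. These are the contrasts of interest and need no equal-correlation assumption. On complete data, an unstructured visit model reproduces them, so little would seem to be gained. This stands for complete pairs, and it also means the completion power is not lost to the trial.

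It does not settle the matter. The mixed model is the only planned analysis that keeps participants with a missing survey, and nothing says which analysis takes precedence. With an assumed 25% of 6-month surveys missing completely at random, the random-intercept 6-month contrast has a type I error of 8.8% under 0.7/0.6/0.5.

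Four stronger readings are tempting, and the documents support none of them:
- A reader might infer that uneven spacing by itself makes the standard errors wrong. It does not: equal correlations at the same visits give ratios of 1.00, and no correlations are stated.
- A reader might apply the 8% to the single PEEPS term. That term gives no separate visit contrasts, and its type I error is 4.0-5.3% under the decaying patterns.
- A reader might infer that a PEEPS effect can never be estimated. That holds for one arm only; with the randomised comparator of Protection of Human Subjects, section 1a, it can be.
- A reader might infer that the definitive trial would inherit wrong variance estimates. The plan does not say that mixed-model covariances will be carried forward, and paired differences give visit-specific SDs directly.

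It is also fair that the plan words the contrast as relative to baseline, which can be read as plain change. The remaining objection is then to the label and the coding.

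**Conclusion.** The point holds in a limited form and is worth correcting before analysis.

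Without any assumed correlation: in the one-arm design the PEEPS coefficient is a before-after change that also contains natural course, regression to the mean and concurrent usual care. As worded, it either merges the two time points of Aim 1 or, beside a visit factor, has no estimate.

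Conditionally: if separate visit contrasts come from the random-intercept model and correlation falls with time, the 6-month test is too liberal (central case about 8%) and the completion test too conservative (about 2.5%). Across the equal and decaying patterns, 6-month type I error runs from about 5% to 9-10%. These figures rest on assumed correlations, equal variances and 40 complete participants.

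The covariance point does not depend on the number of arms: for a between-arm difference in change, the SE ratio is the same. The planned per-visit paired tests remain valid on complete pairs.

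**What to change.** In section 1.3:

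1. Replace the PEEPS term with visit as a three-level factor, and report two contrasts: completion minus baseline and 6 months minus baseline.
2. Use an unstructured within-person covariance with small-sample degrees of freedom. If it does not converge, fall back to a random intercept with small-sample-corrected robust standard errors.
3. State that this model governs, with the paired t-tests as a complete-pairs check. The two agree on complete data, and the model also uses participants with a missing survey.
4. Label the estimate mean change from baseline, not an effect of PEEPS. A richer covariance does not separate PEEPS from time in one arm.
5. Reconcile the synopsis and sections 1.1-1.3 (one arm, three surveys) with Aim 2b (pilot RCT) and Protection of Human Subjects, sections 1a and 1b (usual-care arm, 12-month survey). If two arms apply, add arm-by-visit terms; if the 12-month survey applies, add a visit level.

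The cost is a few lines of text and standard software options. An unstructured covariance for three visits has 6 parameters against 2 for the random intercept, so 4 more, which 40 people with up to three surveys each can support.
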